6.2 Modified Intent to Treat Population (mITT Population)

The mITT population includes all randomized subjects who met all the inclusion and none of the exclusion criteria, have a CEA measurement at baseline (i.e. pre-dose on Day 1), applied at least one dose of study treatment, and have at least one post-baseline measurement for CEA or discontinue due to lack of treatment effect after completing 2 days of treatment.

This population will be used for analyses of superiority.

6.3 Per Protocol Population (PP Population)

The PP population includes all subjects in the mITT population who have no major protocol deviations/violations that would affect the treatment evaluation.

See section 7.5 for more details on protocol deviations and how they affect exclusion from the PP population.

The PP population will be used for analyses of therapeutic equivalence.

7. STATISTICAL METHODS OF ANALYSIS

7.1 General Principles

In general, all data will be listed by treatment group, subject and visit/time-point where appropriate. The summary tables will also be stratified by, or have columns corresponding to, treatment groups.

All subjects will be identified by their unique subject numbers. Data from the screen failures will not be included in tables, listings, or figures.

The total number of subjects in the study group (N) under the stated population will be displayed in the header of summary tables.

Data will be summarized using descriptive statistics for continuous variables. Unless otherwise specified, descriptive statistics will include number of subjects, mean, standard deviation (SD), minimum, median, and maximum. The minimum and maximum statistics will be presented to the same number of decimal places as the original data. The mean and median will be presented to one more decimal place than the original data. The standard deviation will be presented to two more decimal places than the original data. The number of missing observations will be presented only if non-zero.

In summary tables of categorical variables, counts, and percentages will be used. The count [n] indicates the actual number of subjects in a particular category, which should always be less than or equal to the total number of subjects in the respective study group with known (non-missing) category [M]. Percentage will be obtained by: % = n/M*100. Unless otherwise specified, all percentages will be expressed to one decimal place.

All statistical tests will be two-sided at a significance level of $\alpha = 0.05$, unless otherwise indicated. No adjustment will be made for multiplicity.

Unless otherwise specified below, baseline for an assessment will be defined as the last available assessment obtained prior to the first application of the study drug.

In by-visit summaries only scheduled visits/time-points will be presented. Unscheduled assessments will not be included in by-visits summaries, however, will be shown in listings and may be used in selecting the baseline, if applicable.

Relative days will be calculated relative to the date of the first dose of the study medication. Relative days will be calculated as follows only when the full assessment date is known (i.e., partial dates will have missing relative days).

For assessment on or after the day of the first dose of the study drug:

Relative Day = Date of Assessment – Date of First Dose of Study Drug+1.

For assessment before the day of the first dose of the study drug:

Relative Day = Date of Assessment – Date of First Dose of Study Drug.

All dates will be displayed in DDMMMYYYY format.

7.2 Subject Disposition

The number of subjects screened in the study, randomized to treatment, included in the Safety, PP, mITT populations, prematurely discontinued from the study (along with the reasons for discontinuation) will be calculated. The percentages will be based on the number of subjects randomized to each treatment group. Percentages for discontinuation reasons will be based on the sub-population of subjects who discontinued from the study.

Number and percentage of subjects enrolled by site will be tabulated for all enrolled subjects, Safety, mITT, and PP populations.

7.3 Demographic and Baseline Characteristics

Demographic characteristics will include:

• age;

- gender;
- race;
- ethnicity;

Baseline characteristics include:

- Height, weight and BMI;
- Time since rosacea diagnosis (years).
- Baseline CEA score;
- Baseline SSA score:

Descriptive statistics will be presented for age (years), height, weight, BMI and time since diagnosis (years). Frequency counts and percentages will be presented for race, ethnicity, and baseline CEA and SSA score. Height will be reported in centimeters and weight in kilograms.

Age will be derived from Informed Consent Signed Date and Date of Birth as the number of whole years between those two dates.

Demographic and baseline/randomization characteristics will be evaluated for comparability across treatment groups in the following manner. Continuous variables (age, height, weight, BMI, time since diagnosis) will be analyzed with an ANOVA with factors of treatment and investigational site. Overall p-value for the global null hypothesis of all groups being equal will be displayed. Categorical variables (gender, ethnicity, race, CEA and SSA scores) will be analyzed with a Cochran-Mantel-Haenszel, stratified by investigational site. For gender, ethnicity, race, CMH general association statistic will be used. For CEA and SSA scores, "mean scores differ" statistic will be used.

[figure not shown]
All parameters reported during screening or baseline phase (including informed consent information, inclusion/exclusion criteria, randomization information, method of contraception, etc.) will be presented in by-subject listings.

7.4 Medical History

Medical history terms will be coded using MedDRA version 22.0.

Medical and surgical history other than rosacea history will be summarized by MedDRA system organ class, preferred term and treatment group. One subject will be counted only

once under each applicable system organ class and preferred term. System organ classes and preferred terms will be presented alphabetically.

Pooled sites will be used in all the efficacy analyses.

7.6.2 Derivation of the Primary Endpoint

A subject is defined as achieving treatment success at a time-point if the CEA score is at least 2 grades lower than the baseline value of the score. In this case baseline is defined as the predose assessment on Day 1. To achieve the primary endpoint, the subject needs to have treatment success at all 4 post-application timepoints (3, 6, 9 and 12 hours) on Day 29.

The CEA score at all post-application time-points on Day 29 as well as the pre-treatment
assessment on Day 1 are required to determine the primary endpoint.

7.6.3 Analyses of Primary Endpoints

Proportion of subjects achieving the primary endpoint will be presented by treatment.

Also, proportions of subjects with treatment success will be presented by visit (Day 1 or Day 29), time-points and treatment.

7.6.3.1 Analysis of Therapeutic Equivalence of Test and Reference Treatments

Two-sided, continuity-corrected, 90% confidence intervals on the Test-vs-Reference difference for the proportion of subjects with treatment success at all timepoints on Day 29 will be constructed. Therapeutic equivalence will be established if the 90% confidence interval for the difference is contained within the interval [-0.20, +0.20] for the PP population.

7.6.3.2 Analysis of Superiority to Placebo Control

The evaluation of superiority will be conducted separately for the Test treatment versus the Placebo treatment and for the Reference treatment versus the Placebo treatment, comparing the proportions of subjects with treatment success at all time-points on Day 29. The analysis will be conducted using two-sided exact CMH test stratified by site.

Superiority will be established if the success proportion for each active treatment is greater than, and statistically significantly different from (p < 0.05 for the exact CMH test) that of the

Placebo for the mITT population. Analysis of superiority will be performed on the mITT population.

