11.2 Code Fragments

Therapeutic equivalence analysis in the primary endpoint

```
proc freq data=<dataset>
    tables <treatment>*<success> / riskdiffc;
run;
```

Note: this analysis needs to be performed on a dataset containing test and reference treatment subjects only.

Superiority analysis in the primary endpoint

```
ods output ExactTests=ExactTests;
proc logistic data=<dataset>;
  class <treatment> / param=ref;
  model <success> = <treatment>;
  strata <pooled site>;
  exact <treatment>;
run;
```

Note: p-value from exact CMH test is found in ExactTests dataset, variable ExactPValue.

Reference for exact CMH test: http://support.sas.com/kb/32/711.html.

This analysis needs to be performed separately for test and reference treatments on a dataset containing only test and placebo or reference and placebo treatment subjects.

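### Neither primary analysis uses baseline CEA, which fixes the end grade that counts as success; adding it is a small, cheap gain in efficiency and robustness, not a question of validity

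*SAP*

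**What the plan says.** **Endpoint.** SAP 7.6.2 counts success at a time point "if the CEA score is at least 2 grades lower than the baseline value of the score", and the primary endpoint needs this at all four post-application times on Day 29. Protocol 4.1 (criterion 6) requires a CEA grade of 3 or more at baseline, and Table 3-1 of the protocol tops the scale at 4. SAP 6.2 admits to the mITT population only subjects who meet the entry criteria and have a baseline CEA, and the PP population is a subset of it. So every analysed subject has a known baseline of 3 or 4.

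**Superiority (mITT).** SAP 7.6.3.2 conditions on site: "The analysis will be conducted using two-sided exact CMH test stratified by site". The code in SAP 11.2 has "model <success> = <treatment>" and "strata <pooled site>", with no other covariate. The protocol synopsis and Protocol 7.7.1 name the same site-stratified exact CMH test.

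**Equivalence (PP).** SAP 7.6.3.1: "Therapeutic equivalence will be established if the 90% confidence interval for the difference is contained within the interval [-0.20, +0.20] for the PP population". The code is "tables <treatment>*<success> / riskdiffc", a single two-by-two table with a continuity correction and no stratum.

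**Use of baseline CEA.** SAP 7.3 lists "Baseline CEA score" among the baseline characteristics and compares it across arms with a site-stratified CMH statistic. Protocol 7.5 says that baseline comparability will not be tested inferentially. SAP section 8 declares no departures from the protocol's analyses.

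**The concern.** The required improvement is the same for everyone, 2 grades, but the grade that a subject must reach is not. A baseline of 3 has to end at 0 or 1; a baseline of 4 can end at 0, 1 or 2. Success rates may well differ between the two groups.

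If they do, a chance excess of grade 4 subjects in one arm shifts both the Test-minus-Reference difference and the placebo contrasts. An analysis that uses baseline removes that shift and some of the residual variance. The plan instead spends baseline CEA on a significance test of balance, which improves no estimate. Superiority must be shown for each active arm, so power lost on either placebo contrast counts.

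**Working it through.** No sample size, power or assumed success rate is readable in either document, so there is no stated figure to reproduce. The only response rates are in the reference label (Protocol Appendix II, Table 2): 12-18% on active and 5-9% on vehicle per time point. They are for a CEA-and-SSA composite and are not split by baseline grade. Everything below therefore rests on assumed ranges.

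**Assumptions.** Share with grade 4, q: 0.1 to 0.4. Success rates by grade, p3 and p4: differing by 0 to 0.30. Subjects per arm, n: 100 to 400.

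**1. Equivalence interval.** With overall rate p = (1-q)p3 + q·p4, the share of outcome variance explained by baseline is

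R² = q(1-q)(p4-p3)² / [p(1-p)].

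The part of the half-width before the continuity correction scales by √(1-R²).

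- No dependence on baseline: R² = 0, no change.
- q = 0.2, p3 = 0.15, p4 = 0.25: p = 0.17, R² = 0.16 × 0.01 / 0.1411 = 0.011, factor 0.994.
- q = 0.4, p3 = 0.30, p4 = 0.60 (most favourable): p = 0.42, R² = 0.24 × 0.09 / 0.2436 = 0.089, factor 0.955.

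In absolute terms, at n = 200 and p = 0.30 in both arms, the planned 90% half-width is 1.645 × √(2 × 0.30 × 0.70/200) + 1/200 = 0.0754 + 0.005 = 0.080. With R² = 0.07 it is 0.0754 × √0.93 + 0.005 = 0.078. The margin is 0.20.

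**2. Chance imbalance.** The 95% limit of the resulting shift is 1.96 × √(2q(1-q)/n) × |p4-p3|. At its largest (q = 0.4, gap 0.30):

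- n = 100: 1.96 × 0.0693 × 0.30 = 0.041
- n = 200: 1.96 × 0.0490 × 0.30 = 0.029
- n = 400: 1.96 × 0.0346 × 0.30 = 0.020

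With q = 0.2 and a gap of 0.10 at n = 200 it is 1.96 × 0.040 × 0.10 = 0.008.

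**3. Superiority power.** Three exact analyses were run on the same simulated data: 1,500 trials per row, equal site sizes, two-sided p-value ordered by probability. The main-effect model conditions on pooled site and adds baseline CEA as a term.

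| n/arm, sites, q | Active (gr. 3, gr. 4) | Placebo (gr. 3, gr. 4) | Site only | Site × baseline strata | Main effect |
|---|---|---|---|---|---|
| 200, 20, 0.2 | .13, .25 | .05, .11 | 81.0% | 80.3% | 82.5% |
| 200, 20, 0.2 | .13, .13 | .05, .05 | 75.3% | 75.3% | 77.7% |
| 200, 20, 0.3 | .10, .35 | .04, .18 | 75.8% | 78.5% | 80.3% |
| 200, 10, 0.4 | .10, .35 | .04, .20 | 70.4% | 76.4% | 77.9% |
| 160, 20, 0.2 | .25, .45 | .13, .28 | 75.5% | 74.6% | 77.9% |
| 160, 20, 0.3 | .22, .52 | .10, .32 | 83.5% | 85.4% | 88.1% |

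The main-effect model gains from 82.5 - 81.0 = 1.5 to 77.9 - 70.4 = 7.5 points. Simulated type I error was 2.3 to 4.7%. The standard error of a single power figure is about 1 point (√(0.8 × 0.2/1500) = 0.010), so the smallest gain alone is weak evidence; the consistent direction is stronger. The gain in row 2, where baseline predicts nothing, comes from a less conservative discrete null distribution, not from explained variance.

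**4. Sparsity.** Crossing site with baseline is a different matter. With 150 per arm, 20 sites, 20% grade 4 and a non-prognostic baseline (16% versus 6%), power fell from 77.4% to 73.8% in 3,000 simulated trials. With 10 sites at 150 per arm, or 20 sites at 200 per arm, the same set of simulations showed no loss. A separate simulation with 200 per arm, 20 sites and weak prognosis went from 71.8% to 69.7%.

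**The case against.** **Validity is not at stake.** A reader might infer that omitting baseline CEA biases the comparisons or inflates error. It does not: randomization protects the unadjusted error rates. This stands.

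**Baseline does not change the size of the hurdle.** A reader might also infer that severe subjects must improve by more or fewer grades. The documents require the same 2-grade drop of all; only the end grade differs. Whether that makes success more or less likely at grade 4 is not shown anywhere.

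**The gain may be nil.** No rates by grade are given. The upper-end figures assume gaps as large as or larger than the whole active response in the label table. For equivalence this stands: without a prognostic effect, the interval does not narrow.

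**Sparse strata can cost power.** True for full site-by-baseline stratification with many sites, as shown above. It does not carry over to a main-effect term, which leaves the strata as pooled sites.

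**Ignoring the balance test is right.** Agreed: choosing covariates from that p-value would be worse practice. The argument for adjustment is that baseline is plausibly prognostic and known in advance.

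**Parts of the plan cannot be read.** The randomization details are cut (Protocol 7.2, SAP 3.3), as are SAP 7.5 and the start of 7.6. Baseline CEA may have been a randomization stratum. Chance imbalance would then be smaller, but the analysis should still reflect the stratum, and the primary code in SAP 11.2 has no such term.

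**Conclusion.** The point holds as one of efficiency and robustness. Neither primary analysis uses a two-level baseline variable that is complete in both analysis sets and fixes the end grade needed for success.

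For equivalence the benefit is modest: 0 to about 4.5% off the interval width before the continuity correction, and protection against a shift of at most about 3 points at 200 per arm (4 points at 100), against a margin of 20. For superiority it was 1.5 to 7.5 power points in the simulated settings with baseline as a main effect. All sizes depend on the assumed grade 4 share, the gap between grades, the number of sites and n, none of which the readable text supplies.

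Separately, and without any assumption, the baseline tests in SAP 7.3 conflict with Protocol 7.5 and with the statement of no changes in SAP section 8. The change is worth making because it costs little, not because the planned analyses are wrong.

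**What to change.** Before unblinding:

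1. **Superiority.** Extend the exact conditional model to `model success = treatment baseline_CEA; strata pooled_site; exact treatment;`. Do not cross site with baseline grade. State which two-sided exact p-value is used, and stop calling the adjusted test a CMH test.
2. **Equivalence.** Estimate the Test-minus-Reference risk difference with Mantel-Haenszel weights over baseline CEA (3 versus 4), with a 90% interval. The present correction is defined for a single table, so write out the stratified version, for example by adding (1/nT + 1/nR)/2 to the half-width. The estimate stays on the risk-difference scale, so the margin of 0.20 still applies.
3. **Sensitivity.** Keep the two currently planned analyses as prespecified sensitivity analyses.
4. **Consistency.** Reconcile the baseline tests in SAP 7.3 with Protocol 7.5.

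**Cost.** A few lines of code, plus more than SAP wording: the protocol synopsis and Protocol 7.7.1 name the site-stratified exact CMH test and must be amended, and the change must be listed in SAP section 8. If baseline CEA proves not to be prognostic, the equivalence gain is nil.

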7.7 Safety Analyses

7.7.1 Adverse Events

Adverse Events will be coded using the MedDRA Version 22.0 AE coding system for purposes of summarization.

Only Treatment Emergent Events (TEAEs) will be used for the summary analysis. An AE will be considered as treatment-emergent if the time of onset is after the time of the first study drug administration or if it increased in severity during the study period. AEs with unknown start dates will be counted as treatment-emergent unless the AE resolution date is prior to the study drug start date. If the start date is partially missing, then month and year (when available) will be used to determine if the event occurred prior to or post dosing.

Pre-treatment AEs will be listed only.

A TEAE is defined as treatment-related if it is recorded as related to the study medication on the eCRF. In case the relatedness was not assessed, the most conservative result (related) will be chosen for the analysis.

An overall summary will include, by treatment group and overall, the number of TEAEs and the number and percentage of subjects reporting at least 1 TEAE in the following categories:

- Any TEAE
- Treatment-related TEAE
- Serious TEAE
- TEAE leading to discontinuation of the study medication
- TEAE leading to death.

The following TEAE frequency tables will be prepared summarizing the overall number of TEAEs, the number and percentage of subjects reporting at least one TEAE by MedDRA SOC and PT:

- All TEAEs,
- Serious TEAEs

- AEs leading to discontinuation of the study drug
- TEAEs by Severity
- TEAEs by Relationship to Study Drug.

A subject experiencing the same AE (the same preferred term) multiple times will only be counted once for that preferred term. Similarly, if a subject experiences multiple AEs within the same system organ class, that subject will be counted only once in that system organ class. AEs summaries will be presented in alphabetical order of SOC and preferred terms. When summarizing AEs by severity, only the most severe occurrence within the preferred term or system organ class will be used. Similarly, when summarizing AEs by relationship to study drug, only the most related occurrence within the preferred term or system organ class will be selected for displays in summary tables.

Additionally, TEAEs will be summarized by the preferred terms in the descending order of frequency in the total treatment group. In this table a p-value from Fisher's exact test comparing event rates between the Test and the Reference treatment groups will be provided for those preferred terms that have frequency > 1% in either Test or Reference group.

All information pertaining to adverse events noted during the study will be listed by subject, detailing verbatim, preferred term, system organ class, start date, stop date, intensity, outcome, action taken, and causal relationship to the study drug.

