7 STATISTICAL AND ANALYTICAL PLANS

The sections described here highlight the sample size determinations and planned analyses for this study. SAS Version 9.4 or higher will be used to perform all the statistical analyses. A Statistical Analysis Plan (SAP) that expands the statistical section of the protocol will be approved prior to locking the database. The SAP will provide descriptions of the statistical methods, hypotheses, analysis populations to be analyzed, and text with table and listing shells. The SAP will serve as a companion to the protocol and will serve as the de facto documentation of the proposed statistical evaluation.

Version No.: 3.0;

The continuous data will be summarized by treatment groups using descriptive statistics (number of subjects (n), mean, standard deviation (SD), median, minimum, and maximum). Categorical data will be summarized by treatment groups using frequency count (n) and percentages (%).

All statistical tests will be conducted at the 5% significance level, unless indicated otherwise.

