6 ADVERSE REACTIONS

6.1 Clinical Studies Experience

Confidential Page 88 of 102

Protocol No.: OXY2018-01 Version No.: 3.0; 29 JAN 2020

Because clinical trials are conducted under varying conditions, adverse reaction rates observed in the clinical trials of a drug cannot be directly compared to rates in the clinical trials of another drug and may not reflect the rates observed in practice.

A total of 489 subjects with persistent facial erythema associated with rosacea were treated with RHOFADE once daily for 4 weeks in 3 controlled clinical trials. An additional 440 subjects with persistent facial erythema associated with rosacea were also treated with RHOFADE once daily for up to one year in a long-term (open-label) clinical trial. Adverse reactions that occurred in at least 1% of subjects treated with RHOFADE through 4 weeks of treatment are presented in Table 1 below.

Table 1: Adverse Reactions Reported by $\geq 1\%$ of Subjects through 4 Weeks of Treatment in Controlled Clinical Trials

	Pooled Controlled Clinical Trials		
Adverse Reaction	RHOFADE Cream (N = 489)	Vehicle Cream (N = 483)	
Application site dermatitis	9 (2%)	0	
Worsening inflammatory lesions of rosacea	7 (1%)	1 (<1%)	
Application site pruritus	5 (1%)	4(1%)	
Application site erythema	5 (1%)	2 (<1%)	
Application site pain	4 (1%)	1 (<1%)	

In the long-term (open-label) clinical trial, the rates of adverse reactions over a one-year treatment period were as follows: worsening inflammatory lesions of rosacea (3%), application site dermatitis (3%), application site pruritis (2%), application site pain (2%), and application site erythema (2%). Subjects with persistent erythema along with inflammatory lesions were allowed to use additional therapy for the inflammatory lesions of rosacea.

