2. OBJECTIVES

The primary objectives of this study are:

- To establish the therapeutic equivalence between Test Product (Oxymetazoline hydrochloride Cream, 1%, manufactured by Actavis Laboratories, Salt Lake City, UT) and Reference Product (RHOFADETM Cream, 1%, Allergan) on Day 29, in subjects with moderate to severe persistent facial erythema of rosacea.
- To demonstrate superiority of the efficacy of the two active treatments over the placebo control.

The secondary (safety) objective of this study is:

- To monitor adverse events (AEs) and assess the safety and tolerability of Test Product and Reference Product in subjects with moderate to severe persistent facial erythema of rosacea.

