3.3 Randomization and Unblinding Procedures

Subjects will be randomly assigned in a treatment allocation ratio of 1:1:1 to receive the Test product or the Reference Product or the Placebo control, respectively. The randomization schedule for this study will be generated by a third-party vendor such that a non-study-assigned independent expert will allocate the subjects to one of the three treatment arms using a computer-generated automated process,

(respective to that site) will be retained at the study site following the completion of the study and should be available to regulatory authority inspectors at the time of site inspection to allow for verification of the treatment identity of each subject.

The Investigator, staff at the study site, study monitors, and data analysis/management personnel will be blinded to the treatment assigned to the subject. Only the Independent Dispenser will have access to the study medication, but their primary responsibilities will be limited to dispensing, collecting and observing and supervising the administration of the study medication by the subject on clinical visits. They will not participate in any activities.

In case of an emergency, if the details of the study drug are required for management of an emergency as per the opinion of Investigator, the Investigator can unblind the product that is received by the subject during the study.

At the conclusion of the study, after the database has been locked, each site will be sent the study randomization scheme (respective to their site) that should be retained with the study documents in the event of an FDA inspection along with evidence of when the randomization scheme was provided.

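### The only formal Test-versus-Reference safety comparison is a per-term Fisher p-value with no risk difference or interval; it says little at the label's event rates and is not declared as a change from the protocol

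*SAP*

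**What the plan says.** The safety objective in SAP section 2 is to monitor adverse events and "assess the safety and tolerability of Test Product and Reference Product in subjects with moderate to severe persistent facial erythema of rosacea". It sets no margin and no decision rule.

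SAP 7.7.1 tabulates treatment-emergent events by arm as counts and percentages. In the table ordered by frequency it adds one comparison: "a p-value from Fisher's exact test comparing event rates between the Test and the Reference treatment groups will be provided". This is limited by a frequency threshold and appears only "for those preferred terms that have frequency > 1% in either Test or Reference group". The readable text names no risk difference, ratio or confidence interval. The general rule in SAP 7.1 is "All statistical tests will be two-sided at a significance level of" 0.05, and "No adjustment will be made for multiplicity".

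SAP 7.7.2 shows application-site reactions by severity, visit, sign or symptom, and treatment. SAP 7.7.3 and 7.7.4 summarise vital signs and physical examination by treatment. None of the three names a between-product comparison.

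Protocol 6.5.2 (adverse events) and 7.6 (safety assessment) both state that nothing inferential is planned. SAP section 8 states that the analyses do not differ from the protocol's.

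**The concern.** Two things stand out.

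First, the documents do not agree. The protocol rules out inferential safety analysis, the SAP adds a hypothesis test between the two active products, and the SAP then declares no change.

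Second, the added test is a poor summary for rare events. Efficacy equivalence is judged by a 90% confidence interval against a margin of 0.20, so the reader sees what the data exclude. The safety table offers only a p-value. With listed reactions near 1% to 2% per term, a non-significant result is likely even if one cream has twice the rate of the other. A bare p-value shows neither the size of the observed difference nor the size of the difference that remains possible. At stake is how the tolerability table reads beside an equivalence claim. No trial decision depends on it.

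**Working it through.** The readable text gives no power, event count or arm size for safety, so there is no planned figure to reproduce.

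**Inputs**
- Test: two-sided Fisher, alpha 0.05, no multiplicity adjustment (SAP 7.1, 7.7.1).
- Allocation: "Subjects will be randomly assigned in a treatment allocation ratio of 1:1:1" (SAP 3.3), so Test and Reference arms are equal.
- Reference four-week rates (Protocol Appendix II, label section 6.1, N = 489): dermatitis 9/489 = 1.84%; worsening inflammatory lesions 7/489 = 1.43%; pruritus and erythema 5/489 = 1.02% each; pain 4/489 = 0.82%. These agree with the label's rounded values.
- Arm size: redacted. I assume 100 to 500 per arm.

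**Grounds for the assumed range**
- Equivalence, margin 0.20, true difference 0: n = 2p(1−p)(z₀.₉₅ + z₁₋β/₂)²/0.20². With p = 0.05 and 80% power, 2(0.0475)(8.57)/0.04 gives 21. With p = 0.50 and 90% power, 2(0.25)(10.82)/0.04 gives 136.
- Superiority, using the label's Day 29 composite rates as a rough guide: 18% versus 6% at 80% power needs 114 per arm, and 12% versus 6% at 90% power needs 477.
- The label endpoint requires success on both the clinician and subject scales and is reported hour by hour. It is not this trial's endpoint, so the range remains an assumption.

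**Miss rate**

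For arm size n and true rates p_R and p_T, the miss rate is the sum of Bin(x; n, p_T) × Bin(y; n, p_R) over all pairs (x, y) with Fisher p ≥ 0.05. Exact enumeration gives:

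| n per arm | 2% to 4% | 2% to 6% | 1.84% doubled | 1.84% tripled | 1.02% doubled | 1.02% tripled |
|---|---|---|---|---|---|---|
| 100 | 96% | 83% | 96% | 85% | 99% | 96% |
| 200 | 87% | 56% | 88% | 60% | 95% | 82% |
| 300 | 77% | 34% | 80% | 38% | 91% | 69% |
| 400 | 68% | 20% | 71% | 24% | 86% | 55% |
| 500 | 60% | 11% | 63% | 14% | 82% | 43% |

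- For 2% to 6%, power passes 50% at about 225 per arm.
- For 80% power at a 2% Reference rate, a doubling needs about 1,210 per arm and a tripling about 400. A tripling from 1% needs about 830.

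**Smallest significant split**

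With 0 Reference events, 5 Test events give p of about 0.06 and 6 give p of about 0.03, at every size checked from 100 to 500. The rule for showing a p-value is met much earlier: 2/150 = 1.3% already exceeds 1%.

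**What an interval would add**
- 6/150 versus 3/150: Fisher p = 0.50; observed difference 4.0% − 2.0% = 2.0 points; 95% score interval −2.2 to +6.7 points.
- 4/200 versus 4/200: p = 1; the 95% Newcombe interval still runs from −3.3 to +3.3 points.

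**Pooling**

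The label's four application-site rows sum to 9 + 5 + 5 + 4 = 23, and 23/489 = 4.7% if no subject is counted twice. A doubling to 9.4% is missed 82%, 62%, 44%, 29% and 20% of the time at 100, 200, 300, 400 and 500 per arm. A pooled row is more informative than any single term, but it still needs an interval.

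**The case against.** The strongest reply is that the documents never draw the inference that would be wrong. The objective is to monitor and assess, not to show similarity. The p-value feeds no decision, and the protocol treats safety as descriptive. A reader might infer that the SAP takes p > 0.05 as showing comparable tolerability. Nothing in either document says so, and that reading should not be attributed to the sponsor.

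A reader might also infer that the test would miss a tripling at most plausible arm sizes, or that the column will be non-significant whatever the truth. The figures do not support either. At a 2% rate the test detects a tripling more often than not above about 225 per arm, and 89% of the time at 500. Only the doubling result holds across the whole assumed range.

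Three further limits stand. Per-arm percentages let a reader subtract for themselves, and SAP 7.7.2 gives a structured by-arm display of local reactions, so this is the only formal comparison, not the only comparative information. The table shells are in a separate document not available here, so the final columns cannot be seen. Neither document defines what excess of a local reaction would matter clinically, so no such threshold is claimed.

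That safety tables are descriptive does not rescue the bare p-value. A difference with its interval is the descriptive summary; a lone p-value is not.

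**Conclusion.** The point holds as a minor reporting weakness together with an undeclared addition to the protocol.

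The conflict between the protocol's exclusion of safety inference, the added Fisher test and the SAP's declaration of no changes can be read directly from the text and rests on no assumption.

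The low information in the p-value rests on the label's rates and on an assumed 100 to 500 per arm. Over that range a doubling from 2% to 4% is missed 96% to 60% of the time. The tripling result depends on rate and size: at 2% it is missed more often than not only below about 225 per arm, while at about 1% it is still missed 55% of the time at 400 per arm.

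The SAP states no wrong conclusion from the p-value, and no efficacy result is affected.

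**What to change.** - In the SAP 7.7.1 by-frequency table, give the Test minus Reference risk difference with a 95% score or exact interval for each term above 1% in either active arm, in place of or beside the Fisher p-value.
- Add one pooled row, any application-site reaction TEAE, with the same interval, to be read alongside the by-arm table in 7.7.2.
- State that these comparisons are descriptive and that p > 0.05 is not evidence of similar safety.
- Record in SAP section 8 any between-product safety comparison that is kept, since Protocol 6.5.2 and 7.6 plan none.

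The cost is a few sentences of SAP text and a change to one table shell, with no new data and no extra subjects. The downside is that intervals for rare terms will be wide and will look less reassuring than a non-significant p-value.
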